Patient selection is based on the selection, inclusion and exclusion criteria listed below. Patients who meet each of the selection and inclusion criteria and none of the exclusion criteria are eligible to participate in this study.

All patients will receive oral and written information on the study and will sign a written Informed Consent Form (ICF) prior to any study specific assessments and before any data collection is performed.

IV.1.1 - SELECTION CRITERIA

During the selection visit (V0) detailed in section VI.2, the investigator will check that study eligible patients meet all the following selection criteria:

- 1. Male or female patient aged 18 years or older,
- 2. Type 2 Diabetes diagnosed for at least 6 months with a stable authorized antidiabetic therapeutic regimen for 3 months,
- 3. Treated with insulin for at least 6 months,
- 4. Patient with 8.0% ≤ HbA1c <12.0% within the last 3 months before selection,
- 5. Patient with a current minimum of 2 daily insulin injections and who would benefit of an optimisation,
- 6. Patient requiring long term family nurse's daily assistance at home for performing insulin injections and/or glucose monitoring,
- 7. Total daily insulin dose < 1.5U/kg,
- 8. Patient willing and able to complete the requirements of the study,
- 9. Patient living with a caregiver or a diabetes care partner, or patient living alone but with a caregiver living nearby who has a telephone and a key to his or her home,
- 10. Patient living in an area covered by a GSM (Global System for Mobile Communications) network and not considering a trip outside of France or out of an area covered by a GSM network within the planned dates corresponding to the 30 days of the installation of the pump (to cover the open-loop period and first 15 days of the closed-loop period) and the last 20 days of the study.

IV.1.2 - INCLUSION CRITERIA

Before randomisation, the investigator will check that study eligible patients meet all the following inclusion criteria:

- 1. Patient having demonstrated ability to understand the benefits and harms of the automated insulin delivery system and to continuously and safely wear a CGM, as per investigator's judgement,
- 2. Family nurse having demonstrated ability to use the automated insulin delivery system, as per Home Healthcare Provider (HHP) judgement,

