- 3. Patient able to use basic technology such as a cell phone and having demonstrated ability to use the automated insulin delivery system, as per Home Healthcare Provider (HHP) judgment. In case the

patient has not demonstrated ability to use the automated insulin delivery system, his (her) caregiver has to demonstrate ability to use basic technology such as a cell phone and the automated insulin delivery system instead as per Home Healthcare Provider (HHP) judgment. The caregiver has to be an adult person able to speak and read French, having demonstrated ability to use the automated insulin delivery system, with no known medical condition that in the judgment of the investigator might interfere with the completion of the protocol. The caregiver must have committed to maintain uninterrupted availability via personal cell phone and to provide assistance to the patient and must be knowledgeable at all times of the participant's location during the day when closed loop is in use.

- 4. 14 days completed (i.e.≥ 70% of the daily data points non missing) CGM data from the selection period (the CGM period may be repeated only once if uncompleted data),
- 5. Patient covered by healthcare insurance (in accordance with French regulation),
- 6. Patient who has received verbal and written information about the study and who signed the informed consent form before any study related procedure.
- 7. Patient under curatorship must have received the agreement of their legal guardian to participate to the study.

IV.1.3 - EXCLUSION CRITERIA

During the selection visit (V0) detailed in section VI.2, the investigator will check that study eligible patients do not meet any of the following exclusion criteria:

- 1. Pregnant or breastfeeding woman,
- 2. Patient who experienced a severe hypoglycaemic event having led to a hospitalisation or having required a third party assistance within the past 6 months,
- 3. Patient who experienced a diabetic ketoacidosis within the past 6 months,
- 4. Patient who has demonstrated a marked decrease in hypoglycaemia perception defined by a Gold score > 4.
- 5. Patient who has disabilities which could compromise the compliance to the study, in the investigator's opinion,
- 6. Patient with severe health impairment resulting in short life expectancy (< 1 year) as assessed by the investigator,

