The caregiver has to be an adult person, with no known medical condition that in the judgment of the investigator might interfere with the completion of the protocol and who committed to maintaining uninterrupted availability via personal cell phone and to provide assistance to patient. The caregiver must have demonstrated the ability to use basic technology such as a cell phone and to use the automated insulin delivery system as per Home Healthcare Provider (HHP) judgment.

IV.3 - STUDY DURATION FOR THE PATIENT

Trial termination is defined by the date of the last completed visit (actual or planned to be performed at the time of premature withdrawal if applicable) by the last participating patient. The maximum patient's individual study duration will be of 20 weeks.

IV.4 - PREMATURE STUDY DISCONTINUATION

The study could be interrupted temporarily or definitively by the Sponsor and/or the Ethics Committee (EC) and/or the Competent Authority (CA). If such a situation occurs, the investigator should promptly inform the patients and complete the study electronic Case Report Form (e-CRF) with all available data at that time. Study temporary or definitive discontinuation must be declared to Competent Authority (and EC if applicable) in accordance with French local requirements, including its reason such as:

- The investigational intervention is considered as too noxious (as per Ethics Committee (EC) and/or Competent Authority (CA) and/or DSMB (detailed in section IX.3) and/or Sponsor

- A new fact occurs that modifies Sponsor/Competent Authority approval on the trial, such as benefit/risk ratio for instance;
- Any unethical reason;
- Sponsor decision to discontinue the IMD development.

Pharmacovigilance Department recommendation);

Also, patients have the right to withdraw from the study at any time for any reason, without prejudice to further treatment. All the data collected until then will be kept in the study, but not the data collected afterwards.

In addition, the Sponsor or the Investigator may decide to stop the trial or part of the trial at any time for a given patient.

Reasons for individual premature withdrawal recorded by the investigator in the e-CRF will include:

- At least 1 selection or inclusion criterion not met,

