At the end of the selection period, as detailed in section VI.2.1, study patients will be randomly assigned in a 1:1 ratio to either investigational group or control group according to a central computer-generated randomization scheme upon confirmation of their randomisation by their investigator.

The study randomisation numbers will be allocated sequentially according to a central allocation system, i.e., an Interactive Web Response System (IWRS), to limit the possible study group allocation bias. Before confirming the patient randomization, the investigator should record the patient's birth date (month and year), the informed consent signature date, the gender, the HbA1c level and the confirmation of the inclusion/exclusion criteria met.

The randomization will be performed by block and stratified on the HbA1c level (either <10.0% or ≥10.0%).

The patient will be equipped by the IMD attributed by the IWRS according to his/her randomization number. The randomization number will be automatically registered in the e-CRF at the end of the selection period. The patient will be informed by phone by the Investigator of the allocated group (control/investigational). IMD serial number allocated to each patient will be recorded in the e-CRF at the initiation visit (V1) as per the planned IMD dispensation procedure (see section V.4.4).

The randomization list will be generated via SAS® software by an independent statistician (i.e. out of the study team) of the Clinical Research Organization (CRO) delegated by the Sponsor. One signed paper copy and one electronic copy of the randomization list will be stored at the Quality Assurance Unit of the CRO. The randomization list and individual codes will be kept in the strictest confidentiality until the database lock. They will not be accessible to any study team member before the randomisation of a given patient by his (her) investigator. Especially, the randomisation blocks size(s) will not be revealed to any study team member until the database lock, keeping in mind that this block size may be unique for the whole randomisation list or that a combination of 2 or more variable block sizes may have been introduced in the randomization list prior to its computer-generation.

In case of screening failure prior to patient's randomization, the investigator will specify in the patient's eCRF the date and reason for his (her) non-randomization.

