The family nurse will not attend the end of study visit at the hospital. The HHP will contact the family nurse to provide her (him) with information regarding the new patient MDI T2D care as per investigator's prescription.

VI.7 - ASSESSMENTS AND PROCEDURES

VI.7.1 - PATIENT'S ASSESSMENTS AND PROCEDURES

Figure 2: STUDY FLOWCHART of EXAMINATIONS and EVALUATIONS Figure 2A-Investigational Group

| | SELECTION | INITIATION | RUN-IN | | | FOLL | OW-UP | | |
|---|-----------|-------------|---------------|---------------------|----------------------|------------|------------|------------|------------|
| EXAMINATIONS AND EVALUATIONS | VISIT | VIBIT 1 | VISIT 2 | VISIT 3 | VISIT 4 | VISIT 5 | VISIT 6 | VISIT 7 | VISIT 9 |
| | | | D0-D2 | D3 | D9 | D15 | D30 | D60 | D90 |
| Information letter + Informed consent form | Х | | | | | | | | |
| Demographics child-bearing potential (blood pregnancy test) | X | | | | | | | | |
| Medical and surgical history | X | | | | | | | | |
| Physical examination, blood pressure and body weight (and height at Selection) | Х | X | Х | | | | | | Х |
| Cognitive assessment MOCA and/or MMSE | X | | | | | | | | |
| Concomitant medication | X | Х | Х | X | X | Х | Х | Х | Х |
| Fundus examination | X | | | | | | | | |
| Selection, Inclusion and Non Inclusion criteria | X | Х | | | | | | | |
| Randomisation | Х | | | | | | | | |
| Laboratory data: HbA1c, blood glucose, total cholesterol, triglycerides, HDL-C, | v | | | | | | | | |
| LDL-C, serum albumin, creatinine, AST, ALT, blood counts, gamma GT | X | Х | | | | | | | Х |
| CGM system | | | | 0 | | | | | |
| Patient equipment & training | | X | | | | | | | |
| CGM replacement by family nurse | Х | Х | | Х | Х | Х | Х | Х | |
| CGM removal | | | | | | | | | Х |
| Remote monitoring | Х | Х | | | | | | | |
| Pump System | | | | | | | | | |
| Patient equipment & training | | X Open mode | X Closed-loop | | | | | | |
| Catheter changes & cartridge fill in, battery charge | | Х | X | X | X | X | Х | Х | X |
| Remote monitoring | | | | Х | Х | | Х | Х | Х |
| Pump system removal | | | | | | | | | Х |
| Home Healthcare Provider Services | | | | | 10 10 | | | | |
| Patient 24/7 technical support and motivation | Х | Х | Х | Х | Х | Х | Х | Х | Х |
| Family nurse training | Х | Х | | Х | | | | | |
| Patients, Caregivers training and motivation | Х | Х | Х | Х | | | | | |
| Pump data upload and follow-up | | | Х | X byfamily nurse | X by family nurse | | х | Х | Х |

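### Figure 2 marks the eligibility check again at Visit 1, after the arm is known; read with IV.4 and X.2.1, this makes arm-aware removal from the primary analysis possible

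*Combined protocol and SAP*

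**What the plan says.** **Before randomisation.** IV.1.2 opens: "Before randomisation, the investigator will check that study eligible patients meet all the following inclusion criteria". IV.1.3 sets the exclusion check at the selection visit (V0), where "the investigator will check that study eligible patients do not meet any of the following exclusion criteria". V.5 says what the investigator records before confirming randomisation, including "the HbA1c level and the confirmation of the inclusion/exclusion criteria met". The synopsis agrees: assignment follows validation of the criteria.

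**Timing of allocation.** V.5 states: "At the end of the selection period, as detailed in section VI.2.1, study patients will be randomly assigned in a 1:1 ratio". The investigator then tells the patient the arm by phone. V1 comes later and starts treatment in groups that are already randomised (VI.3). The trial is open-label (III).

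**At V1.** Figures 2A and 2B mark the row "Selection, Inclusion and Non Inclusion criteria" under Selection and again under V1, in both arms. Randomisation is marked under Selection only. The investigator's V1 tasks in VI.3.1 contain no eligibility check.

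**Consequences of failure.** The IV.4 withdrawal reasons include "At least 1 selection or inclusion criterion not met". Exclusion criteria are not named. A patient withdrawn for a listed reason before D3 is replaced by another patient in the same arm.

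**Analysis sets.** X.2.1 defines the safety set as randomised patients still participating when V1 ends. It draws the modified ITT set, which carries the primary analysis, from the safety set. X.2.1 also lists departures from the selection, inclusion and exclusion criteria among the protocol deviations to be reviewed before database lock.

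**The concern.** The randomised comparison is protected when eligibility is settled before anyone knows the arm. Removing a randomised patient later as ineligible is harmless only if the decision rests on facts from before randomisation, with equal scrutiny in both arms and without knowledge of the arm. The flowchart puts a second check where the arm is known, IV.4 supplies a ground for removal, and nothing in the plan guarantees equal or blinded scrutiny.

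A patient removed at V1 is outside the safety set and therefore outside the modified ITT set. The replacement enters a predetermined arm rather than by chance. If such removals followed prognosis differently in the two arms, the primary TIR comparison would no longer be between the groups as randomised. No planned efficacy analysis uses the Randomised ITT set, so no other result would show the effect.

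**Working it through.** **1. Does the V1 mark come after allocation?** Yes. Randomisation closes the selection period and is marked only in the Selection column. In Figure 2B, V1 is D0. In Figure 2A, V1 precedes the run-in visit, which is D0 to D2. V1 is therefore after randomisation and before D3 in both arms.

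**2. Does the IV.4 ground reach randomised patients?** The list mixes pre- and post-randomisation reasons; too little CGM data after a repeated selection recording is a screening failure. But replacement within an arm has meaning only for a patient who already has an arm. As written, the rule is not confined to patients awaiting randomisation.

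**3. Does removal at V1 change the primary set?** Yes, through X.2.1, by the chain safety set to modified ITT set. The synopsis differs: it draws the modified ITT set from all randomised patients with sufficient CGM at baseline and at D70 to D90. A patient who left at V1 would usually lack the second recording and fall out under that wording too.

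**4. The plan's own sample size.** Inputs from X.1: difference 17, SD 16, two-sided alpha 5%, power 90%, 10% added for adjustment, 25% non-evaluable.
- n = 2 × (16/17)² × (1.960 + 1.282)² = 18.6, rounded up to 19 per arm
- 19 × 1.10 = 20.9, rounded up to 21
- 21 / 0.75 = 28 per arm, 56 in total

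This reproduces the stated figure, which is not in dispute.

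**5. Illustration of size.** The documents give no rate of eligibility failure at V1, so everything here except the SD and the arm size is assumed. Suppose k of 28 patients are removed in one arm only, their expected TIR is d SDs below the arm mean, and average patients replace them. Then

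shift in arm mean = (k/28) × d × 16

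| k | d = 0.5 | d = 1 |
|---|---|---|
| 2 | 0.57 | 1.14 |
| 3 | 0.86 | 1.71 |

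The range is 0.6 to 1.7 points, or 3.4% to 10.1% of the planned 17.

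For an unadjusted z test with 21 evaluable patients per arm, SE = 16 × √(2/21) = 4.94. If the same shift carries over to the evaluable patients, the two-sided type I error of nominally 5% becomes 5.2% at a shift of 0.57 and 6.4% at 1.71. Adjustment for baseline TIR would reduce this to the extent that baseline TIR carries the prognosis.

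**The case against.** The strongest reply is that this is a stray mark in a flowchart. The synopsis, IV.1.2, IV.1.3 and V.5 agree that eligibility is settled before randomisation, VI.3.1 describes no V1 check, and the figure does not say that a failed check removes anyone. IV.4 may have screening failures in mind. X.2.1 already treats eligibility departures as protocol deviations, lists them for all randomised patients and tabulates them in the modified ITT set, so the plan expects some such patients to stay. X.4 reports withdrawals by arm in the Randomised ITT set, which makes removals visible.

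Much of this stands. The V1 check rests on the figure alone. Many criteria are facts fixed before randomisation, such as duration of insulin treatment and CGM completeness in the selection period, and the row is marked in both arms. What does not fall away is that IV.4 replaces within an arm and X.2.1 drops patients who leave by the end of V1. An unmet criterion is thus a deviation in one section and a ground for removal in another. Reporting withdrawals shows a problem but does not restore the comparison.

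A reader might infer more: that the plan directs selective removal by arm, or that scrutiny at V1 is demonstrably unequal because only the device arm has a 48-hour stay. The documents support neither. No passage states such a practice, and the stay is observation after the pump start, with its own withdrawal provision in VI.3.1. Nor does IV.4 support reading a failed exclusion criterion as a ground for withdrawal, since it does not name exclusion criteria.

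**Conclusion.** The inconsistency is real and worth correcting. As written, the rules leave room for randomised patients to be removed from the primary analysis by someone who knows the arm, and for non-random replacement. This is a possibility that the plan leaves open, not a practice that it prescribes.

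The size cannot be estimated from the documents. The 0.6 to 1.7 points are an illustration that assumes one-sided removal of 2 to 3 patients with poorer prognosis, and they are small against 17. They should not be read as an expected bias. The case for change rests on the low cost of closing the gap, not on a demonstrated distortion.

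**What to change.** 1. Reconcile Figures 2A and 2B with IV.1.2, V.5 and VI.3.1, so that the final eligibility check for trial entry comes before the IWRS call.
2. In IV.4, limit an unmet selection or inclusion criterion, as a ground for withdrawal and replacement, to patients not yet randomised.
3. State that a criterion found unmet after the IWRS call is a protocol deviation under X.2.1, affecting membership of the PP set only.
4. Amend X.2.1 so that the modified ITT set is drawn from all randomised patients rather than from the safety set, as the synopsis already words it. Continue to collect D70 to D90 CGM from these patients where they agree; without it the CGM requirement would still remove them.

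Safety assessment at V1, and whether a patient continues on the device, remain clinical decisions outside this rule.

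The cost is wording in Figure 2, IV.4 and X.2.1, plus CGM collection for a few patients. The downside is that a few ineligible patients stay in the primary analysis; the planned PP analysis addresses that.

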- Physical examination including cognitive assessment (MoCA and/or MMSE score at selection visit only).

VI.7.1.4 - **TREATMENTS**

T2D treatment history

History of T2D treatments (trade name, start/end date) will be collected at selection visit. Patients must have been treated with insulin for at least 6 months prior to their selection visit. Patients prescription for daily insulin treatment and glycaemic control by a home family nurse will be collected at selection. Patients must require daily home nurse care for their insulin treatment at the time of their selection visit.

Concomitant medication

Current treatments (trade name, start/end date) for comorbidities will also be collected at each visit performed at hospital.

- Insulin

Insulin (trade name, start/end date) used during the study will be collected. Of note, the automated insulin delivery system is intended to be used with U100 Humalog® or NovoRapid® rapid-acting insulin analogues only.

- IMD use (for patients in the investigational group only)

Time on auto-mode defined as the percentage of time spent with activated closed-loop of the insulin administration system over 24-h day will be computed based on the data continuously recorded into the Pump. In addition, patient compliance to the IMD will be collected at each visit by the investigator both on patient medical file and in the e-CRF by asking questions to the patients and checking the patient diary. The reason for any non-compliance, including treatment and/or study discontinuation will be recorded in both patient medical file and e-CRF by the Investigator.

VI.7.1.5 - FUNDUS EXAMINATION OR RETINAL PHOTOGRAPHY

Patients with proliferative retinopathy can not be included in the study. If the last fundus examination or retinal photography examination is dated more than 6 months, a new fundus examination or retinal photography will be requested by the investigator. The examination must be performed before randomisation.

VI.7.1.6 - **Pregnancy Test**

A blood pregnancy test will be performed at selection visit for women of child-bearing potential.

VI.7.1.7 - LABORATORY DATA

The following assessments will be performed at Selection, Initiation and End of study visits:

- Glycaemic control: blood HbA1c, blood glucose.
- Lipid profile: total cholesterol, triglycerides, HDL-Cholesterol, LDL-Cholesterol.
- Hepatic function: serum albumin, AST, ALT, gamma GT.
- Kidney function: serum creatinine.

 Blood counts (Red Blood Cells (RBC), White Blood Cells (WBC), platelets, haemoglobin, and hematocrit).

VI.7.1.8 - GLYCAEMIC CONTROL AND GLYCAEMIC VARIABILITY

In addition to HbA1c assays, the glycaemic control and variability will be computed based on the continuous measurement of the glucose values recorded after wearing the CGM device in blinded mode during the 14 consecutive days of the selection period and every day from D70 to D90.

VI.7.1.9 - Adverse Events/Device Deficiencies/Failure

Safety assessments will consist in evaluating all serious and non-serious adverse events (AE), and device deficiencies/failure occurring from the Informed Consent Form (ICF) signature until the end of the study.

At each visit, occurrence of AEs and device deficiencies/failure should be inquired and follow-up of previously reported AEs and device deficiencies/failure should be performed. Related essential data should be recorded in the patient's medical file and in the e-CRF by the Investigator.

For the AEs, the following data will be recorded in the e-CRF:

[figure not shown]
- Description of the AE
- Seriousness of the event
- Onset and resolution dates of the AE
- Severity of the AE (mild, moderate or severe)
- Causality with regards to IMD
- Causality with regards to investigation procedures
- Action(s) taken regarding the IMD Corrective treatment/therapy given Event outcome.

In addition, the following parameters will be considered for assessment of the safety profile of automated insulin delivery system:

[figure not shown]
- Hypoglycaemic events defined as at least 10 min of continuous CGM readings below the thresholds of (1) 70 mg/dL (3.9 mmol/L) or (2) 54 mg/dL (3.0 mmol/L),
- Non severe hypoglycaemic events, being defined by CGM readings between < 70 mg/dL (3.9 mmol/L) and ≥ 54 mg/dL (3.0 mmol/L),
- Severe hypoglycaemic events being defined by CGM readings < 54 mg/dL,
- Severe hypoglycaemic events requiring third party assistance,
- Severe hypoglycaemic events requiring hospitalization,
- Severe hyperglycaemic events being defined by CGM readings ≥ 300 mg/dL for over 1 hour, Device incidents and deficiencies.

A Data Safety Monitoring Board (DSMB) will review the safety data of the five first patients of each group, then 25 patients having completed the study, and more frequently if judged necessary by the DSMB.

[figure not shown]

[figure not shown]

VII - ENDPOINTS

VII.1 - PRIMARY ENDPOINT

The primary endpoint will be Time In Range (TIR) at D90, defined as the percentage of time spent with CGM glucose measurements at 70-180 mg/dL (including boundaries), during the last 14 days completed of CGM recording between D70 and D90 at the end of the study period.

For any of the 14 days to be eligible, \geq 70% of the data points have to be non missing. Full 24-hour periods available only will be used, thus excluding from the calculation all days with CGM sensor installation or desinstallation.

For data analysis and calculation of the TIR at baseline and at D90, gaps in the CGM recording for incomplete days will be imputed using a linear interpolation approach of the planned 14 days [51].

The primary endpoint will be computed at D90 for the full 24-h day. In a complementary way, the TIR will also be computed separately considering the diurnal period (from 06.00 H to 23.59 H) and the nocturnal period (from 00.00 H to 05.59 H).

VII.2 - SECONDARY ENDPOINTS

VII.2.1 - EFFICACY ENDPOINTS

- HbA1c absolute change from baseline: HbA1c will be assayed for all patients at baseline and
 D90. The absolute change from Baseline, i.e., HbA1c at D90 HbA1c at Dbaseline will be calculated for each patient.
- Absolute change of glucose variability from baseline:
- ullet The percentage coefficient of variation (%CV) will be computed at baseline (%CV_{Basl}) and D90 (%CV_{D90}), as well as the absolute difference (%CV_{D90}-%CV_{Basl}) for each patient [52]. For a given patient, the %CV_{Basl} will be calculated by dividing the Standard Deviation (SD) by the corresponding mean of the CGM recordings during the 14 days at the end of the selection period.

In the same manner, for each patient, the %CV_{D90} will be calculated by dividing the Standard Deviation (SD) by the corresponding mean of the CGM recordings during the last 14 days of the D70 to D90 period.

[figure not shown]
For each patient, $\%CV_{Basl}$, $\%CV_{D90}$ and the ($\%CV_{D90}$ - $\%CV_{Basl}$) difference will be computed 3 times:

- Considering the full 24-h day,
- ⇒ the diurnal period (from 06.00 H to 23.59 H),
- or the nocturnal period (from 00.00 H to 05.59 H) separately,
- Absolute change of Time In Range from the 14 days completed CGM recording at the end of the selection period (baseline) to the last 14 days completed CGM recording from D70 to D90 at the end of the study period: time in range is defined in section VII.1 as the percentage of time spent in target range of glucose level (CGM measurements in 70-180 mg/dL (including boundaries)). At baseline, as well as from D70 to D90, any day of the considered period need to have ≥ 70% non missing data points to be eligible for the TIR computation. The absolute change in TIR from Baseline, i.e., D90-D0 will be calculated 3 times for each patient: (1) for the full 24-h day, (2) for the diurnal period (from

[figure not shown]

06.00 H to 23.59 H) and (3) for the nocturnal period (from 00.00 H to 05.59 H),

- Time below target range is defined as the percentage of time spent with CGM glucose measurements (1) <70 mg/dL, and (2) <54 mg/dL, during the last 14-day CGM completed recording from days 70 to 90. The time below target range will be computed for the full 24-h day, the diurnal period (from 06.00 H to 23.59 H) and the nocturnal period (from 00.00 H to 05.59 H) separately,
- Time above target range is defined as the percentage of time spent with CGM glucose measurements (1) >180 mg/dL, and (2) ≥250 mg/dL, during the last 14-day CGM completed recording from days 70 to 90. The time above target range will be computed for the full 24-h day, the diurnal period (from 06.00 H to 23.59 H) and the nocturnal period (from 00.00 H to 05.59 H) separately,
- Total daily insulin dose change from baseline to D90 (sum of basal and bolus insulin injection), Body weight absolute change from baseline (end of period of selection) to D90.

VII.3.1 - SAFETY PARAMETERS

Safety assessments are detailed in section VI.7.1.9. They include:

- Number of diabetes-related hospital admissions and their length of stay: the frequency of scheduled and unscheduled diabetes-related hospital admissions will be calculated for each study patient from baseline to D90.
- Number of hypoglycaemic events
- Number of diurnal hypoglycaemic events (i.e., occurring from 06.00 H to 23.59 H)
- Number of nocturnal hypoglycaemic events (i.e., occurring from 00.00 H to 05.59 H)
- Number of non severe hypoglycaemic events
- Number of severe hypoglycaemic events
- Number of severe diurnal hypoglycaemic events (i.e., occurring from 06.00 H to 23.59 H)
- Number of severe nocturnal hypoglycaemic events (i.e., occurring from 00.00 H to 05.59 H)
- Number of severe hypoglycaemic events requiring third party assistance
- Number of severe hypoglycaemic events requiring hospitalization
- Number of severe hyperglycaemic events (≥ 300 mg/dL for over 1 hour).

[figure not shown]
Adverse events and device deficiencies/failure will be collected from the signature of the informed consent to study end.

A Data Safety Monitoring Board (DSMB) will review the safety data of the five first patients of each group, then 25 patients having completed the study, and more frequently if judged necessary by the DSMB.

Composition, role and frequency of DSMB meetings will be detailed in the separate DSMB Charter.

VII.3.2 -

VIII - SAFETY AND DEVICE DEFICIENCIES

VIII.1 - DEFINITIONS

Adverse Event (AE)

Any untoward medical occurrence, unintended disease or injury, or untoward clinical signs (including clinically significant abnormal laboratory findings) in patients, users or other persons, whether or not related to the investigational medical device.

This definition includes events related to the procedures involved (see definition below).

For users or other persons, this definition is restricted to events related to investigational medical devices.

Investigation Procedure

Any procedure specific to the clinical investigation. All activities related to the use of a medical device may be considered investigation procedures.

Note: "Preceding investigation procedure" shall be understood as a procedure which is imposed by the Clinical Investigation Plan and which has taken place before (or coincided in time) with the serious adverse event.

Adverse Device Effect (ADE)

Adverse Event related to the use of an investigational medical device.

This definition includes adverse events resulting from insufficient or inadequate instructions for use, deployment, implantation, installation, or operation, or any malfunction of the investigational medical device.

This definition includes any event resulting from use error or from intentional misuse of the investigational medical device.

Abnormal laboratory value

All abnormal laboratory values that the investigator is aware of will be reported as Adverse Events if the investigator categorizes their values as « Clinically Significant » (CS).

Serious Adverse Device Effect (SADE)

Adverse Device Effect that has resulted in any of the consequences characteristic of a Serious Adverse Event.

SAEs related to procedures imposed by the clinical investigation plan but not with the use of the device should not be considered Serious Adverse Device Effects.

Serious Adverse Event (SAE)

Adverse Event that led to any of the following: -

death

- serious deterioration in the health of the patient, that either resulted in:
- a life-threatening illness or injury, or

- a permanent impairment of a body structure or a body function, or
- in-patient or prolonged hospitalization, or
- medical or surgical intervention to prevent life-threatening illness or injury or permanent impairment to a body structure or a body function, or
- chronic disease,
- foetal distress, foetal death or a congenital physical or mental impairment or birth defect.

Note: planned hospitalization for a pre-existing condition, or a procedure required by the protocol, without serious deterioration in health, is not considered as a Serious Adverse Event.

The following reasons for hospitalization are exempted from being reported:

- Hospitalization for social and/or convenience reasons.
- Hospitalization for pre-planned (i.e., planned prior to signing informed consent) surgery or standard monitoring of a pre-existing disease or medical condition that did not worsen.

However, complications that occur during hospitalisation are AEs or SAEs (for example, if a complication prolongs hospitalization).

Use Error

Act or omission of an act that results in a different medical device response than intended by the manufacturer or expected by the patient.

Use Errors include slips, lapses, and mistakes.

Note: an unexpected physiological response of the patient does not in itself constitute a Use Error.

Device Deficiency

Inadequacy of a medical device with respect to its identity, quality, durability, reliability, safety or performance.

Note: Device Deficiencies include malfunctions, use errors, and inadequate labelling.

Unanticipated Serious Adverse Device Effect (USADE)

Serious Adverse Device Effect which by its nature, incidence, severity or outcome has not been identified in the current version of the Risk Analysis report.

Note: Anticipated Serious Adverse Device Effect (ASADE) is an effect which by its nature, incidence, severity or outcome has been identified in the Risk Analysis report.

VIII.2 - COLLECTION, ASSESSMENT AND FORWARDING REPORTING BY THE INVESTIGATOR

VIII.2.1 - COLLECTION AND ASSESSMENT

All Adverse Events (serious and non-serious, related and not related) and device deficiencies occurring during the study from the informed consent signature until the end of study i.e., the last study evaluation will be reported by the investigator in the e-CRF. Related SAEs may be reported at any time.

Adverse Events, ADEs and Device Deficiencies will be entered by the Investigator in the corresponding section of the e-CRF. SAEs, ADEs and Device Deficiencies will be reported by the Investigator by the means of specific forms. Depending on the situation, both forms may have to be used for a single event.

- The Investigator will assess the seriousness of every Adverse Event.
- The Investigator will assess the causal relationship between each adverse event and the Investigational Medical Device and/or investigation procedures. That causal relationship is assessed as being a reasonable possibility or not. A reasonable possibility of a causal relationship between the event and the Investigational Medical Device and/or investigation procedures means that there are facts (evidence) or arguments to suggest a causal relationship. If a causal relationship is suggested between the event and the Investigational Medical Device, the Adverse Event meets the definition of the Adverse Device Effect.
- The Investigator will assess, for every device deficiency, if it could have led to a SADE, if appropriate action had not been taken, intervention had not occurred, or circumstances had been less fortunate.

VIII.2.2 - REPORTING TO THE SPONSOR

The investigator reports to the sponsor, immediately and no later than 3 calendar days of his/her being aware, all SAEs, ADEs and Deficiencies of the Investigational Device and/or investigation procedures, by the means of, respectively the "SAE/ADE Form" and/or the "Device Deficiency Form", that will be sent by email to:

AIR LIQUIDE Santé INTERNATIONAL, Pharmacovigilance Department:

Email: [contact]

The investigator will answer within 48 hours to any safety query sent by the sponsor.

VIII.2.3 - ASSESSMENT BY THE SPONSOR

For each Serious Adverse Event, the sponsor (Study Physician) will assess the causal relationship between the investigational medical device and/or investigation procedures and the event.

For each device deficiency, the sponsor (Study Physician) will assess if that device deficiency could have led to a SADE, if appropriate action had not been taken, intervention had not occurred, or circumstances had been less fortunate.

The assessments given by the investigator cannot be downgraded. In case of disagreement, both opinions are provided.

VIII.2.4 - REGULATORY SAFETY SUBMISSIONS BY THE SPONSOR

Regulatory safety submissions (individual cases, annual safety reports) will be done by the sponsor according to legal requirements.

VIII.3 - NEW SAFETY EVENTS

A new safety event is any new data which might lead to:

- A reassessment of the benefit-risk balance of the study or of the IMD,
- A change in the use of the IMD, in the conduct of the study, or in the study documents,
- The interruption, discontinuation or modification of the study protocol or other study conducted on the same IMD.

Any new safety event occurring during the study period will be notified by the Sponsor according to legal requirements to the French Competent Authority and Ethics Committee.

IX - DATA HANDLING

IX.1 - ELECTRONIC CASE REPORT FORM (E-CRF)

An electronic data capture system will be used for this study. An electronic CRF (e-CRF) will be designed to collect all the data required by the protocol apart from the automatic recordings of the study IMDs. The e-CRF will be developed by the Information Technology Department of ICTA (Dijon, France), in compliance with Sponsor specifications and regulatory requirements.

Data entry will be performed by the Investigator or by the designated person from his/her team at the investigator site and by the HHP with two different connection profiles, using the e-CRF screens designed with web technologies.

Patients will be identified with a unique identification code. Two letters for the country code, three digits for the site number, dash then the patient number on 3 digits. The last 3 digits will be attributed according to the chronological order of selections within each centre.

Data entered *via* the Internet will be directly recorded in the SQL study database.

The investigator or the designated personnel from his/her team agrees to complete all documents provided by the Sponsor at each patient's visit and complete the e-CRF as close as possible from the patient's visit.

